The study is a collaboration between researchers from the Laboratory of Molecular Cardiology (LMC) Department of Cardiology, Rigshospitalet, Department of Biomedical Sciences, University of Copenhagen, Department of Medical Endocrinology,

Rigshospitalet, and Department of Endocrine Diseases, Department of Medicine, Herlev-Gentofte Hospital.

Purpose

The purpose of the study is to characterize patients who are being treated or have been treated for Graves' disease and have been euthyroid for a minimum of three months, but despite this experience cardiac symptoms.

Patient characteristics include:

- Medical history and symptoms
- Biochemical analyses
- A cardiac workup: resting 12-lead ECG, 24-hour ambulatory electrocardiogram monitoring (Holter analysis), transthoracic echocardiography, and an exercise stress test
- Phenotype/genotype variations

No deviations from standard treatments will be made in the study.

Hypothesis

The hypothesis is that Graves' disease in genetically predisposed individuals will induce cardiac changes that persists months to years after normalization of thyroid hormone concentrations in the blood. This is a previously undescribed condition that could be caused by a remodeling of myocardial tissue and of the autonomic nervous system.

Rationale for the study

Euthyroid patients with a persistent tendency to dyspnoea, intermittent palpitations, and increased heart rate – after treatment of Graves' disease – may have a previously undescribed "syndrome" (cf. textbooks and literature in the reference list (page 19)).

Genetic analyses and statistical considerations

We will use the Polygenic Risk Score (PRS), developed on genetic data from the Næstved Cohort (see page 9) and other cohorts to try to predict who is genetically predisposed to e.g. sinus node and contractile dysfunction. The genetic variants included will be selected

using an algorithm that tries to ensure that each genetic variant is independent. Here, the so-called "pruning and thresholding" method is used [Khera AV 2018].

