3. Transthoracic echocardiography (ultrasound of the heart). The examination provides anatomical information about the pericardium, myocardium, ventricles, heart valves and central vessels, as well as quantitative information about the myocardium's pumping ability, haemodynamics and valve function. The recordings are blinded and analyzed by supervising echocardiographer and consultant [name].
4. The exercise stress test is performed as a physical load test on an ergometer bike with standardized increase (25W at start, 25W increase every 2 minutes) of the workload while simultaneously monitoring symptoms, blood pressure and 12-lead

ECG before, during and after the test. The investigation shall be conducted in accordance with the protocol available on Cardio.dk. The purpose of the study is to assess the development of arrhythmias, the functioning of the autonomic nervous system and work capacity. The maximum heart rate and time to this, resting heart rate, and time from max heart rate to resting heart rate are measured.

Genetic analyses

3 x 9 ml of blood is drawn for genetic analyses. The blood is transferred to EDTA glass and glass with Trasylol and frozen and stored at -80 degrees. Purification of DNA is performed at the Laboratory of Molecular Cardiology, Rigshospitalet Heart Center, using the Maxwell 16 LEV blood DNA Kit (sold by Promega; Wisconsin, USA). Later, genotyping is carried out using ChIP technology at the *Institut für Klinische Molekularbiologie, Universitätsklinikum*, Schleswig-Holstein, Kiel, Germany. This is not a whole-genome sequencing study. The study aims to investigate single nucleotide polymorphisms (SNP) in specific regions of the genome. The study uses SNP-array/SNP genotyping, where the analysis is based on general genetic variation and not mapping of the genome. The results are used to map risk loci and to determine plausible disease-causing genes. The study will give an understanding of the most common variants in Graves' patients, and with the possibility of comparing these with the Næstved cohort and the United Kingdom Biobank (UKBB) as well as being able to compare the variants with control groups. The aim of the study is to determine the significance of the sum of genetic variants' for the development of disease, called the Polygenic Risk Score.

Excess biological material is sent back to Denmark when the analyses in Germany have been carried out. The material is then stored in a biobank, see page 10.

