The purpose of the visit is to check whether the potential participant meets the criteria for participating in the study and to inform the participant about the study prior to any consent. The potential participant has received a telephone call prior to the visit (see above) where the questionnaire is discussed. Furthermore, the trial participant has received written information on the study (appendices 1 and 2). The informative visit and examinations can be carried out during the same visit, which takes place at the LMC. This is provided that

the participant gives his/her consent immediately after the informative meeting. If the potential participant wishes 24-hour reflection time another meeting will be arranged for blood tests and ECG. The duration of the meeting is approximately 1 hour and includes:

- 1) Oral information, clarification of any questions
- 2) Conversation about informed consent and 24-hour reflection time
- 3) The signature of informed consent is ensured before any examinations
- 4) Questions concerning:
 - Inclusion and exclusion criteria
 - Medical history related to Graves' disease (onset, duration, treatment, family history, associated Graves' orbitopathy, smoking)
 - Medicine
 - Symptoms
 - Other diseases
- 5) Further classification of cardiac symptoms through a questionnaire regarding grading of the symptoms.
- 6) Objective examination including blood pressure, height, and weight
- 7) Blood samples for biochemical and genetic analysis
- 8) 12-lead resting ECG

Visit 2:

The visit takes place at LMC, lasts approximately 1 hour, and includes:

- 1) Echocardiography
- 2) Attachment of ECG electrodes connected to a recorder for 24-hour ambulatory electrocardiogram (Holter)

Visit 3:

The visit takes place at the Cardiology Outpatient Clinic, Section 2003, Rigshospitalet. It lasts approximately 1 hour and includes:

- 1) exercise stress test

Visit 4:

The visit takes place at the Endocrinology Clinic, lasts approximately 1 hour, and includes:

- 1) Information about the results of the cardiac examinations
- 2) Conversation about the possibilities of drug treatment

Visit 5:

The visit takes place at the Endocrinology Clinic, lasts approximately 1/2 hour, and includes:

- 1) Information about the results of the genetic tests
- 2) Follow-up

Study duration

Recruitment of patients will start as soon as ethical approval is obtained from the research ethics committee. The study is expected to be completed within 5 years.

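### The only heart-rate recovery measure, time from maximum back to resting rate, can understate slow recovery; a fixed-time fall from the same ECG would mend this cheaply.

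*Protocol*

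**What the plan says.** Item 4 of the protocol's list of paraclinical cardiac studies states that one aim of the exercise stress test is to assess "the functioning of the autonomic nervous system and work capacity", besides arrhythmias. It then lists the heart-rate variables: the maximum and how long it takes to reach it, the rate at rest, and finally "time from max heart rate to resting heart rate are measured". The last of these is the only heart-rate recovery variable named.

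Monitoring covers symptoms, blood pressure and "ECG before, during and after the test". The item does not say how long recovery is recorded, how close to the resting value counts as back at rest, or what is recorded for a patient who does not get there. Procedure is deferred to an outside document: "The investigation shall be conducted in accordance with the protocol available on Cardio.dk". Under Study design, Visit 3 is given about one hour.

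The Hypothesis section names remodelling of the autonomic nervous system as one of two possible causes. The Rationale describes the proposed syndrome as "Euthyroid patients with a persistent tendency to dyspnoea, intermittent palpitations, and increased heart rate", and an increased heart rate is one of the qualifying symptoms in the Inclusion criteria. Item 2 of the same list adds a second autonomic measure, heart rate variation on the 24-hour Holter.

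**The concern.** A time-to-rest measure has two weaknesses in this population.

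- **Missing because of the outcome.** The time exists only if the patient returns to rest while still being monitored. If recording ends first, the missing values fall mostly on the slow recoverers, whom the test is meant to find.
- **A target that moves with the phenotype.** The end point is each patient's own resting rate. A patient whose resting rate is raised has a shorter way to go, so the same recovery kinetics give a shorter time.

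Both push the same way, towards apparently faster recovery. At stake is the exercise test's evidence on one of the study's two proposed mechanisms.

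**Working it through.** The protocol gives no figure for heart-rate recovery, so there is nothing to reproduce. The check tests the mechanism under stated assumptions; none of the recovery figures below comes from the protocol.

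**Model.** Heart rate falls exponentially from maximum to resting rate with time constant tau. Time to within a tolerance c of rest is

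T = tau × ln((max − rest) / c).

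Assumed: maximum 170 (SD 12), rest 70 (SD 10), c = 5 beats/min, tau log-normal with log-SD 0.3 and **median** 2.0 min in one group and 2.5 min in the other.

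**1. Non-return.** With unlimited monitoring the mean times are 6.24 and 7.80 min, a difference of 7.80 − 6.24 = 1.56 min. If only patients who reach rest within the monitoring window are analysed:

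| Window (min) | Back at rest, tau 2.0 | Back at rest, tau 2.5 | Observed difference (min) | Share of 1.56 lost |
|---|---|---|---|---|
| 6 | 51% | 24% | 5.06 − 4.77 = 0.29 | about 81% |
| 10 | 96% | 83% | 0.99 | about 37% |
| 15 | 99.9% | 98.9% | 1.48 | about 5% |
| 20 | 100% | 99.9% | 1.56 | under 1% |

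Taking 2.0 and 2.5 min as means instead of medians, 57% and 29% are back within 6 min, and the loss is about 79% at 6 min and 32% at 10 min. Also widening c to 10 beats/min gives 58% and 10%.

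**2. A second model.** Here the recovery plateau scatters around the resting rate (SD 5), maximum is 172, rest 75, and median tau is 80 or 120 s with log-SD 0.4. Then 40% to 68% are not back within 5 min and 18% to 27% not within 10 min. At 5 min the mean tau of those without and with a value is 109 v 72 s (median 80) or 150 v 89 s (median 120), so the missing values do concentrate in slow recoverers. About 16% are still not back at 30 min because their plateau stays more than 5 beats above rest. In this last group tau is no longer than in the others.

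**3. Resting rate.** Same kinetics, tau 2.0 min, maximum 170, c = 5:

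- rest 60: 2.0 × ln(110/5) = 6.18 min
- rest 90: 2.0 × ln(80/5) = 5.55 min

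That is 10% shorter. With maximum 175 and tau 100 s the times are 314 and 283 s, again 10%. If instead the curve settles at 60 whatever the resting value, moving rest from 65 to 90 cuts the time from 314 to 134 s, or 57%. That case needs a resting value well above the recovery plateau.

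**4. The alternative.** The fall t minutes after peak is (max − rest) × (1 − exp(−t/tau)). At t = 1 and tau = 2.0 it is 110 × 0.393 = 43 beats for rest 60 and 80 × 0.393 = 31 beats for rest 90, a drop of 27%. In beats, then, the fall depends on resting rate more than the time does. Divided by (max − rest), it is 39% in both cases. In the model of step 1 the standardised difference between the groups is 0.75 for this share, against 0.71 for time to rest without censoring and 0.40 for time to rest with a 6-minute window.

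**The case against.** The strongest reply is that the loss depends on a window nobody has stated. The outside procedure may fix a recovery period, and the wording also fits recording until rest is reached. The visit leaves room: starting at 25 W and adding 25 W every 2 minutes, completing the 200 W stage takes 8 × 2 = 16 minutes of about an hour. At 15 to 20 minutes the loss in the first model is 5% or close to nothing. This stands, and it rules out quoting any one percentage as the effect in this study.

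Next, bias arises only if patients who do not return are dropped. The protocol does not say that they will be, and censored times are ordinary matter for an analysis plan, which is not at hand. This also stands. What is left is the choice of variable, which the protocol makes itself.

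A reader might go further and infer that the measure hides autonomic dysfunction. The document does not support that. T is proportional to tau, so slower recovery gives a longer time wherever it is observed. The resting-rate effect is modest if recovery settles at the resting rate, and resting and maximum rate are both recorded, so it can be examined. Holter heart rate variation gives a second view of autonomic function.

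Finally, the fall in beats is no cure for dependence on resting rate. That is correct. Only the share removes it, and exactly so only under the assumed model.

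**Conclusion.** The point holds as a cheap improvement, not as an error in the plan. The one recovery variable named can be unobserved in slow recoverers if monitoring ends before rest is reached, and it shortens by about 10% as resting rate goes from 60 to 90 beats/min if recovery settles at that rate. It can therefore understate slow recovery.

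The size is not known from the document. Under assumed exponential recovery to the resting rate, with median time constants of 2.0 and 2.5 min and non-returners dropped, about 80% of the group difference is lost at 6 minutes, 37% at 10 and about 5% at 15, with less beyond. The direction is the same in every setting tried; the size turns on the window, the tolerance and the handling of non-return. The 80% figure belongs to a 6-minute window and should not be read as the expected loss. No stated sample size rests on this variable.

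**What to change.** In item 4 of the paraclinical cardiac studies, add the heart-rate fall at 1 and 2 minutes after peak, read from the post-test ECG already recorded. Make the share of (maximum minus resting rate) the main form and beats a secondary form, since the fall in beats itself depends on resting rate. Both have a value for every patient whose recording runs 2 minutes past peak.

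If time to resting rate is kept, treat non-return by the end of monitoring as a censored time and report how many did not return. For that, state which resting value is used, how close counts as back at rest, and how long recovery is recorded, or point to where the outside procedure says so.

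The cost is a sentence or two in the protocol and a little extra reading and analysis, with no new procedure. It is best settled before testing, because a recording that ended too early cannot be extended afterwards.

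### The polygenic score has two stated targets, and against general-population controls a score capturing Graves' susceptibility could look positive with no cardiac predisposition

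*Protocol*

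**What the plan says.** Only the protocol is available. Four places bear on the point.

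- **Hypothesis.** The claim is that "Graves' disease in genetically predisposed individuals will induce cardiac changes". The predisposition in question is to cardiac change, given Graves' disease.
- **Genetic analyses and statistical considerations.** The score, developed in the Næstved and other cohorts, is used "to try to predict who is genetically predisposed to e.g. sinus node and contractile dysfunction". This is a cardiac target, given by example. The power paragraph that follows refers to thyrotoxicosis as an instance of multifactorial disease and assumes 80 cases and 200 controls. It does not describe those controls.
- **Genetic analyses (under Examination methods).** The aim is to establish the significance of the summed variants "for the development of disease, called the Polygenic Risk Score". The disease is not named. Shortly before, the text says: "The study will give an understanding of the most common variants in Graves' patients", and it goes on to comparisons with Næstved, UK Biobank and control groups.
- **Comparison with the Næstved cohort.** The heading names Graves' patients from that cohort as the comparator. The body gives 20,000 genotyped members of a general population of 70,000, quotes the incidence of Graves' disease there, and calls the cohort a control. UK Biobank, with 457 Graves' patients, serves for verification and for comparison with similar patients.

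Under Inclusion criteria, every participant has Graves' disease and at least one cardiac symptom. No comparator of Graves' patients without cardiac symptoms is defined.

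**The concern.** A score for sinus node or contractile dysfunction and a score for Graves' disease answer different questions. Only predisposition to cardiac change, among people who already have Graves' disease, bears on the hypothesis.

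The second statement of the aim leaves the target open, and the text around it points towards Graves' disease. If the analysis follows that statement and uses the general population as control, case status and Graves' status almost coincide. A raised score in participants could then mean only that they have Graves' disease, and the analysis could not separate this from a cardiac predisposition. What is at stake is whether the central genetic result can be interpreted.

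**Working it through.** **The protocol's own figure.** There is none for the score. The only power statement (80% for an odds ratio of 5, 80 cases, 200 controls, alpha 0.05) concerns a single variant. It gives no allele or carrier frequency, so it cannot be reproduced as stated; a two-sided comparison of carrier proportions reaches 80% at a control frequency of about 2.5%. It does not settle the score's target.

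**Inputs.**
- Cases: 80 (power paragraph).
- Controls n0: 20,000 (Næstved section) or 200 (power paragraph).
- Alpha: 0.05, taken as two-sided; the protocol does not say.
- Shift d of a Graves' susceptibility score in cases: not in the protocol. Assumed odds ratio per SD of 1.3 to 1.5, so d = ln(1.3) = 0.26 to ln(1.5) = 0.41 SD.
- Cardiac predisposition: none, by construction.

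**Formula.** z = d / sqrt(1/80 + 1/n0); probability of p<0.05 ≈ Φ(z − 1.96).

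- n0 = 20,000: sqrt(0.0125 + 0.00005) = 0.1120
- n0 = 200: sqrt(0.0125 + 0.005) = 0.1323

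| d (SD) | n0 = 20,000 | n0 = 200 |
|---|---|---|
| 0.26 | z = 2.34, 65% | z = 1.98, 51% |
| 0.41 | z = 3.62, 95% | z = 3.07, 87% |

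Over a wider assumed range, d = 0.2 to 0.6 SD, the probability runs from 43% to above 99% against 20,000 and from 33% to 99.5% against 200.

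**Same score, Graves' comparators.** If participants and comparators carry the same Graves' susceptibility, d = 0 and the rate stays near 5%.

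**Price of Graves' comparators.** The difference detectable with 80% power is (1.96 + 0.84) × sqrt(1/80 + 1/n0).

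- General population, 20,000: 2.80 × 0.1120 = 0.31 SD.
- UK Biobank Graves' patients, 457: 2.80 × sqrt(0.0125 + 0.00219) = 2.80 × 0.1212 = 0.34 SD.
- Næstved Graves' patients: 20,000 × 25/100,000 per year × 20 years = 100. This assumes constant incidence, full follow-up and a representative genotyped subset. Then 2.80 × sqrt(0.0125 + 0.01) = 2.80 × 0.15 = 0.42 SD.

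Comparators not selected on symptoms dilute the contrast. If 38% of them have persistent cardiac symptoms (the protocol's survey) and score like the participants, the observed difference is 0.62 of the difference from symptom-free patients. The latter must then be 0.34/0.62 = 0.55 SD (UK Biobank) or 0.42/0.62 = 0.68 SD (Næstved). With no symptomatic comparators the figures stay at 0.34 and 0.42.

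**The case against.** The strongest reply is that no second score is stated. The disease in the Genetic analyses section is undefined, and the sentence may be a generic description of what a polygenic score is. The condition under study is itself called a syndrome, so the word could mean that. The one place that says what the score predicts names cardiac traits, and the remarks on common variants in Graves' patients may concern single variants rather than the score. Score construction is also commonly left to the SAP.

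Much of this stands. A reader might infer that the protocol plans a Graves' susceptibility score in flat contradiction of the cardiac one. The documents do not support that: no such score is announced, and the cardiac target is itself given only by example. A reader might also infer that a raised Graves' score would be reported as support for the hypothesis. The protocol contains no such decision rule.

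A further reply is that the comparator causes the problem more than the label of the score does. That is right. Even a cardiac-trait score can differ between Graves' patients and the general population if the two share genetic causes, so renaming the score would not be enough. It would also be too strong to say that only the cardiac score can ever bear on the question.

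What does not fall away is that the protocol states the aim two ways and the comparator two ways. One available combination of these cannot test its hypothesis. That is a conflict in the stated aim, and an SAP would inherit it.

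**Conclusion.** The point holds as an unresolved ambiguity in the score's target, made consequential by an unresolved comparator. Followed literally (all cases with Graves' disease, general-population controls, a score for the development of an unnamed disease that can be read as Graves'), the analysis could not tell Graves' susceptibility from cardiac predisposition.

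The percentages in the table illustrate the size; they are not predictions. They rest on the assumed shift, on a score that captures Graves' susceptibility, and on the general population as comparator. With Graves' patients as comparator the problem largely disappears. It should be settled before the genotypes are analysed, because it changes what a positive result can mean.

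**What to change.** Reconcile the three sections of the protocol:

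1. In Genetic analyses, name the disease or trait. State that the score testing the hypothesis is the cardiac-trait score (sinus node and contractile function) already given under Genetic analyses and statistical considerations.
2. State that a raised Graves' susceptibility score against the general population is expected, is descriptive, and is not evidence for the hypothesis.
3. In the Næstved section, bring heading and body into line. Use the already genotyped Graves' patients (Næstved, and the 457 in UK Biobank) as comparator for the hypothesis test, and keep the general population as a descriptive reference. Say which group the 200 controls in the power paragraph are.

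The cost is a few sentences, with no new participants, visits or genotyping. The comparator group becomes smaller, its cardiac symptom status may be unknown, and the contrast may be diluted as shown above. A raised Graves' score can no longer be claimed as support.

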Analyses of participants are compared with analyses of Graves' patients from the Næstved cohort

- The trial participants with Graves' disease will undergo genotyping and the results of this will be compared with findings of variants determined in 20,000 of a general population of 70,000 individuals (the Næstved cohort which has been followed over 20 years) in which the incidence of Graves' disease is about 25 out of 100,000 per year (The project is approved in VEK SJ-114). The Næstved cohort is an already genotyped (SNP-genotyped, not whole-genome) cohort of patients. Members of our research group are the managers of the Næstved project. Therefore, it is in our

interests to compare genetic variants found in Graves' patients with a control cohort that we already know and have previously genotyped. Consent is not obtained from the participants of the Næstved cohort because no new studies of the participants' genome are carried out. Thus, there are no health consequences for the Næstved cohort's patients' participation in this project, nor elements of a research perspective that the patients must consider.

- Variants found are further verified using data from the UKBB on about 500,000 individuals. The UKBB contains clinical and genetic data on 457 patients with Graves' disease. There is no question of importing biological material from these patients. Through a data agreement with UKBB, our research group has access to anonymised patient information on British individuals. This includes SNP genotyping, MRI scans, ECGs, etc. Hereby, the data agreement enables us to compare our results with similar patients.

Biobank

Blood samples will be pseudoanonymized and stored for later supplementary genetic, biochemical, histological, and other pathoanatomical studies. Thus, a research biobank will be established in connection with the project. At the end of the project, the biological material will be stored in a fully anonymized manner at the Laboratory of Molecular Cardiology in a conventional biobank. The biological material will be stored for 20 years and will only be included in further research projects with the consent of the participants or with an exemption from the consent given by the research ethics committee. The data protection rules are complied with when any type of biological material is stored in our biobank.

Study design

Visit 1: Informative visit, anamnesis, and paraclinical examinations

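### The protocol names two genetic comparators without assigning either to a question and does not identify its 200 controls; a single-variant difference from the general population is not, alone, evidence of cardiac predisposition

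*Protocol*

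**What the plan says.** All references are to the Protocol; no SAP is at hand.

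- **Section on the Næstved comparison.** The heading is "Analyses of participants are compared with analyses of Graves' patients from the Næstved cohort". The first bullet says that the participants' genotypes will be "compared with findings of variants determined in 20,000 of a general population of 70,000 individuals", and that the aim is to "compare genetic variants found in Graves' patients with a control cohort that we already know and have previously genotyped".
- **Same section, second bullet.** Variants are verified in the UK Biobank (UKBB), about 500,000 people. "The UKBB contains clinical and genetic data on 457 patients with Graves' disease", and "the data agreement enables us to compare our results with similar patients".
- **Genetic analyses.** "The results are used to map risk loci and to determine plausible disease-causing genes". This section also mentions control groups without defining them, and gives the study's aim as the polygenic risk score.
- **Hypothesis.** "Graves' disease in genetically predisposed individuals will induce cardiac changes that persists" after thyroid hormone levels are back to normal.
- **Genetic analyses and statistical considerations.** The polygenic score is meant to predict who is "genetically predisposed to e.g. sinus node and contractile dysfunction". The power statement takes 80 cases, 200 controls, alpha 0.05 and a standard deviation of 10, and claims 80% power for an OR of 5. It does not say who the controls are.
- **Inclusion criteria.** Every participant has Graves' disease and at least one cardiac symptom.

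**The concern.** The heading and the bullet name groups that answer different questions. Comparing participants with other Graves' patients holds Graves' disease constant, so it speaks to the hypothesis, which concerns who develops lasting cardiac change given Graves' disease. Comparing them with a general population does not hold it constant. A variant can then differ because it predisposes to Graves' disease, because it predisposes to cardiac change, or both, and that contrast alone cannot tell these apart.

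At stake is how single-variant results are interpreted. If the bullet governs and a variant found this way is put forward as a cardiac risk locus, the claim may really be about Graves' susceptibility. Separately, a power statement whose control group is not identified does not say which contrast it supports.

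**Working it through.** **1. Who the 200 controls could be.** Groups that the protocol describes, or that follow from its figures:

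| Group | Size | Source |
|---|---|---|
| Genotyped Næstved members | 20,000 | stated |
| UKBB Graves' patients | 457 | stated |
| Graves' cases among the 20,000 | about 100 | 20,000 × 25/100,000 per year × 20 years |
| Graves' cases among all 70,000 | about 350 | 70,000 × 25/100,000 × 20 |

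None is 200. The last two rows are projections, not counts: they assume constant incidence, full follow-up and a random genotyped subset, and leave out cases prevalent at entry. The budget does not fund new control genotyping either: the DNA line is 16,000/200 = 80 analyses, the number of cases. On these figures about 100/20,000 = 0.5% of the population group has Graves' disease, against 100% of cases.

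**2. The plan's own power figure.** A two-proportion test, two-sided 0.05, 80 v 200 people, OR 5, gives power of 52%, 74% and 96% at control carrier frequencies of 1%, 2% and 5%. The stated 80% is met at about 2.5% (about 1.2% if alleles are counted). No frequency is given, so the figure can be neither confirmed nor refuted. At an assumed 2%, changing only the control count gives 58% (100), 74% (200), 83% (457) or 90% (20,000).

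**3. How often a Graves'-only variant would be flagged against the population.** Assumed: allele test, 160 v 40,000 alleles, control allele frequency p0 = 10–30%, no cardiac effect. The case frequency is p1 = OR·p0/(1 − p0 + OR·p0). Power = Φ((p1 − p0 − z·s0)/s1), with s0 the pooled and s1 the unpooled standard error.

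Example, p0 = 0.20, OR 1.5: p1 = 0.30/1.10 = 0.2727; difference 0.0727; s0 = 0.0317; s1 = 0.0353.
- Alpha 0.05 (z = 1.960): Φ(0.300) = 62%.
- Alpha 0.05/1,000 (z = 4.056): Φ(−1.584) = 5.7%.

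| Graves' OR | Bonferroni, assumed 1,000 variants | Unadjusted 0.05 |
|---|---|---|
| 1.2 | under 1% | 13–20% |
| 1.5 | 3–7% | 45–70% |
| 2.0 | 32–64% | 88–99% |

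Against Graves' comparators who differ in nothing else, the rate stays near 5% at alpha 0.05 (simulated: 4.8–5.0% with 100, 5.0% with 457).

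**4. What a Graves'-to-Graves' contrast costs.** Detectable allelic OR, 80 cases, 80% power, allele frequency 20%:

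| Controls | Alpha 0.05 | Alpha 0.05/1,000 |
|---|---|---|
| 20,000 | 1.65 | 2.26 |
| 457 | 1.73 | 2.45 |
| 200 | 1.82 | 2.70 |
| 100 | 1.97 | 3.13 |

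These assume symptom-free comparators. The background section's survey puts persistent symptoms at about 38% of Graves' patients. If 38% of comparators are symptomatic, their allele frequency is 0.38·p1 + 0.62·p0. With a true symptom OR of 2 and p0 = 0.20, p1 = 0.333 and the comparators have 0.251, so the observed OR is (0.333/0.667)/(0.251/0.749) ≈ 1.5. Over p0 = 10–30%, power at alpha 0.05 is then 27–49% with 100 comparators and 41–67% with 457; under Bonferroni it is at most about 5%. At p0 = 20%, the true OR needed for 80% power is about 3.0 (100) or 2.4 (457) at alpha 0.05, and about 6.4 or 4.4 under Bonferroni.

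**The case against.** **Both groups may be intended.** The Næstved bullet describes a population and gives the Graves' incidence in it, and the UKBB bullet likewise moves from about 500,000 people to 457 Graves' patients. The text can be read as planning a population comparison and a Graves' comparison. This stands: the wording does not prove that the Graves' comparison was dropped. What is missing is the assignment of comparator to question.

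**A reader might infer that the genetic analysis as a whole is confounded, or that the sponsor will report Graves' variants as cardiac variants.** The protocol supports neither. Its stated aim is the polygenic score, which targets cardiac traits and is less exposed. A population comparator suits the descriptive aim of finding common variants in Graves' patients. No sentence says that single variants will be read as cardiac predisposition.

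**The large flag rates are assumed.** The 88–99% needs an OR of 2 and an unadjusted 0.05. The protocol gives 0.05 for planning, not as the threshold for an array scan. This stands; under correction the problem is negligible for small effects.

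**The 200 may be a sample of the 20,000.** This is not excluded, and the power statement would then be conservative relative to using all 20,000. But the protocol does not say so.

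**It belongs in the SAP.** Analysis detail does. A heading and bullet that disagree about the comparator, and a power statement without an identified control group, are matters of the protocol's own text.

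**Conclusion.** The point holds in a limited form. The protocol names two comparators, assigns neither to a question, and does not identify the 200 controls. For single variants, the population contrast alone cannot support a claim about cardiac predisposition given Graves' disease. UKBB could supply the missing check, but the text does not say that verification is Graves'-to-Graves'.

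The harm depends on how such variants are interpreted. Its size rests on allele frequencies, Graves' ORs and a number of tests that the protocol does not give. With correction it is small for modest Graves' ORs and becomes material around 2.0 or under lenient thresholds. It would be wrong to conclude that the polygenic score is invalid, that the population contrast should go, or that a Graves'-to-Graves' contrast would settle the question: that contrast removes one explanation and has little power. Severity: minor to should-fix.

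**What to change.** 1. Reconcile heading and bullet by naming the comparator for each question.
2. Keep the general-population contrast for describing variants in Graves' patients, and state that no variant will be interpreted as cardiac predisposition on that contrast alone.
3. For that interpretation, add participants versus the Graves' patients identifiable among the genotyped Næstved members, the 457 UKBB Graves' patients, or both, with ancestry and array differences handled. Report it as a diluted, low-power contrast whose null result does not rule out a cardiac effect.
4. State who the controls in the power statement are, and restate the power for their actual number.

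**Cost.** Protocol wording, plus a check on whether Graves' status is recorded for the genotyped Næstved members, which the protocol does not state. If it is not, the UKBB patients are the only Graves' comparators left. The price in power is real: measured from the 20,000 that the bullet names, the detectable OR rises from 1.65 to 1.73 or 1.97 before dilution, and more after it. The protocol does not say that either source records persistent symptoms or three months of euthyroidism, so the dilution may not be removable. Clinic-recruited participants aged 18–55 may also differ from cohort Graves' patients in other ways, so some selection differences would remain.
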